7 STATISTICAL METHODS

7.1 General Methodology

Data will be analyzed by Precision for Medicine biostatistics personnel. Statistical analyses will be reported with tables, figures, and listings, presented in rich text format, and using recommended ICH numbering. Output specifications for all tables, figures, and listings will be in conformance with guidelines specified by the ICH in Appendix 7 of the *Electronic Common Technical Document Specification* (Apr 2003).

7.1.1 Reporting Conventions

Tables and figures will be summarized by treatment group. Tables summarizing demographics and other baseline characteristics will also include a column for all subjects combined. In general, all data collected and any derived data will be presented in subject data listings for all randomized subjects except for the screening failures listing which will be presented for only screen failures and the informed consent and eligibility criteria listing which will be presented for all screened subjects. Listings will be ordered by treatment group, subject number, and assessment or event date. The treatment groups will be displayed in the same order as they appeared in the summary tables. The treatment group presented in safety listings will be based on the actual assignment. The treatment group presented in all other listings will be based on the planned assignment, unless otherwise noted.

In general, continuous variables will be summarized to indicate the study population sample size (N), number of subjects with available data (n), mean, SD, median, 25th (Q1) and 75th (Q3) quartiles, minimum, and maximum values. Categorical variables will be summarized by the population size (N), number of subjects with available data (n), number of subjects in each category, and the percentage of subjects in each category. Unless otherwise noted, the denominator to determine the percentage of subjects in each category will be based on the number of subjects with available data. The denominator for percentages for incidence data (such as adverse events) will be based on the number of subjects in each category, as appropriate.

7.1.2 Analysis Visit Window

For efficacy analyses and safety analysis by visit, assessments at scheduled and unscheduled visits will be mapped to the appropriate analysis window as detailed in Table 3 and Table 4. In the event where more than one visit falls in the same analysis window, the following rules will be used in sequence to determine the record that will be analyzed:

- If there is a scheduled visit in the analysis window, then the scheduled visit's data will be used.
- If there is no scheduled visit in the analysis visit window, the data closest to the scheduled day/time visit will be used.
- If there is no scheduled visit in the analysis visit window and there is a tie between the visits with regards to the number of days/hours before and after the scheduled day, the later data will be used.

Visit windows will not apply to listings. All data will be included in subject listings.

Windowing will be applied to the data prior to any missing data calculations.

Confidential

Period	Screening	Baseline	Study Drug Treatment Safety Follow-up					ollow-up
Visit	1	2	3	4	5	6		
	Days –7 to –28	Day 1	Day 15 (±2 d)	Day 29 (±2 d)	Day 43 (±2 d)	Day 57 (±2 d)	Day 71	Day 85
Analysis Visit Name		Baseline *	Week 2	Week 4	Week 6	Week 8	Week 10	Week 12
CGI-I HADS	NA	≤1 Pre- dose	[2, 22]	[23, 36]	[37, 50]	[51, 71]	NA	NA
HAMD-17 HAM-A SHAPS		≤ 1 Pre-						
	NA	dose	NA	[16, 43]	NA	[44, 71]	NA	NA
CGI-S	NA	≤1 Pre- dose	NA	NA	NA	[44, 71]	NA	NA
SDS	NA	≤1 Pre- dose	NA	[23, 36]	[37, 50]	[51, 71]	NA	NA

Table 3Analysis Windows for Efficacy Analyses

* Baseline for analysis visit refers to baseline value for efficacy analysis defined in Section 7.1.5

Period	Screening	Baseline	s	Study Drug Treatment				ollow-
Visit	1	2	3	4	5	6		
	Days -7 to -28	Day 1	Day 15 (±2 d)	Day 29 (±2 d)	Day 43 (±2 d)	Day 57 (±2 d)	Day 71	Day 85
Analysis Visit Name		Baseline	Week 2	Week 4	Week 6	Week 8	Week 10	Week 12
Vital signs Clinical laboratory tests COWS	NA	≤1 Pre- dose	[2, 22]	[23, 36]	[37, 50]	[51, last dose +30]	NA	NA
Body weight ECG	NA	≤1 Pre- dose	NA	[2, 43]	NA	[44, last dose +30]	NA	NA
Standard Ophthalmologic examination	NA	≤1 Pre- dose	NA	[2, 14]	NA	≥ 15	NA	NA
Corneal specular microscopy	NA	≤1 Pre- dose	NA	NA	NA	NA	NA	≥2
C-SSRS	Nominal	≤ 1 Pre- dose	[2, 22]	[23, 36]	[37, 50]	[51, 64]	[65, last dose +30]	NA

Table 4Analysis Windows for Safety Analyses by Visit

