6.4.2.8 Ophthalmologic Examination

The following ocular assessments are performed, using these standard clinical operating procedures, at specified visits, on both eyes of each subject:

- 1. Standard Ophthalmologic Examinations: performed at Screening/Baseline, between post-dose days 7-15, and at end of treatment/Week 8.
- 2. Corneal Specular Microscopy (CSM): noncontact or contact specular microscopy for qualitative and quantitative examination of the central corneal endothelium (cell count, cell shape, density, and morphology), with image capture at Screening/Baseline and 12 weeks following first dose.

Local investigators assess and record the results of items 1 and 2 on the examination worksheet. For both the standard ophthalmologic examination and CSM, an assessment of normal/abnormal is captured as well as whether the abnormal result is clinically significant or not. CSM results are sent to **second second** where the designated ophthalmology expert will review. Additional ophthalmologic examinations (standard ophthalmologic exams and/or corneal specular microscopies) may be conducted at any time during the study to assess subject safety.

The final ocular examination for corneal specular microscopy is conducted approximately 12 weeks (+2 days) after the first dose of study drug (including both subjects who complete the study and subjects who discontinue early from the study).

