6.4.2.9 Suicidal Ideation/Suicidality

Suicide-related events (behavior and/or ideation) are assessed and evaluated at every scheduled and unscheduled visit with the administration of the C-SSRS (Posner 2007). The C-SSRS captures the occurrence, severity, and frequency of suicide-related thoughts and behaviors during the assessment period. The 2009 "Baseline" version is used at Visit

BlackThorn Therapeutics, Inc.	Statistical Analysis Plan
K2-MDD-201	Version 2.0; 03 June 2022

1 (Screening), evaluating past year and past 3 months, and the 2009 "Since Last Visit" version is used for all subsequent visits.

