7.5.4 Clinical Laboratory Evaluation

All descriptive summaries of laboratory results will be based on data analyzed by the central laboratory and presented in Système International (SI) units, as suggested by the Center for Biologics Evaluation and Research and the Center for Drug Evaluation and Research *Position on Use of SI Units for Lab Tests* (Oct 2013). All data will be included in by-subject data listings. Laboratory measurements identified as abnormal (ie, outside the normal range) will also be listed separately.

BlackThorn Therapeutics, Inc.	Statistical Analysis Plan
K2-MDD-201	Version 2.0; 03 June 2022

Clinical laboratory measurements, including serum chemistry and hematology, will be summarized by treatment group. Descriptive statistics will be presented for observed values and changes from baseline at each visit where parameters were scheduled to be collected per the clinical study protocol.

Where applicable, laboratory results will be classified as "low," "normal," or "high" with respect to the parameter-specific reference ranges (ie, below the lower limit of the normal range, within the normal range, or above the upper limit of the normal range). Three-by-three contingency tables will be presented for each laboratory parameter to summarize the shift from the baseline category to the worst post-baseline measurement, defined as the value numerically farthest outside of the normal range across all post-baseline visits through the end of the study. Summary results will include the count and percentage of subjects within each shift category and treatment group.

The number and percentage of subjects with a PCS (potentially clinically significant) laboratory result for the select analytes listed below in

will be presented by treatment group and study visit. PCS laboratory results will also be listed.

Analyte	PCS Cutoffs
Hemoglobin	Low:< 10.0 g/dL; < 6.2 mmol/L; <100 g/L
	High: > 2 g/dL (20 g/L) above ULN or above baseline if
	baseline is above ULN
Platelets count	<75,000/mm3; <75.0 x 10e9 /L
WBC count	<3000/mm3; <3.0 x 10e9 /L
Neutrophils	<1500/mm3; <1.5 x 10e9 /L
Lymphocytes	Low: < 800/mm3; < 0.8 x 10e9 /L
	High: >4000/mm3 - 20,000/mm3; > 4 x 10e9 /L - 20 x 10e9 /L
Total bilirubin	> 1.5 x ULN
AST	> 3.0 x ULN
ALT	> 3.0 x ULN
Alkaline phosphatase	> 3.0 x ULN
Creatinine	> 1.5 x above baseline; > 1.5 x ULN
Sodium	Low: < 130 mmol/L
	High: > 150 mmol/L
Potassium	Low: < 3.0 mmol/L
	High: > 5.5 mmol/L
СК	> 5 x ULN
GGT	>2.5 x ULN

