7.5.5 Vital Signs, Physical Findings, and Other Observations Related to Safety

7.5.5.1 Vital Signs

Vital signs will include pulse (supine and standing), systolic/diastolic blood pressure (supine and standing), respiratory rate, body temperature, height, weight, and BMI will be listed by treatment group, subject, and visit date. Vital sign parameter measurements will be summarized by treatment group. Descriptive statistics will be presented for results and change from baseline at each visit where parameters were scheduled to be collected.

The number and percentage of subjects with a PCS measurement in supine will be presented by treatment group and study visit. PCS measurements include systolic blood pressure $\leq 90 \text{ mmHg}$, systolic blood pressure $\geq 180 \text{ mmHg}$, diastolic blood pressure $\leq 50 \text{ mmHg}$, diastolic blood pressure $\geq 105 \text{ mmHg}$, heart rate $\leq 40 \text{ bpm}$, and heart rate $\geq 120 \text{ bpm}$. PCS measurements in supine will also be listed.

Additionally, the number and percentage of subjects with an orthostatic systolic BP decrease > 20 mmHg or diastolic BP decrease > 10 mmHg from supine to standing position at any post-baseline measurement during the study will be summarized and listed.

7.5.5.2 12-Lead Electrocardiogram

Twelve-Lead ECG interval parameters including heart rate, PR, RR, QRS, QT, QTc interval calculated using the Fridericia method (QTcF), and QTc interval calculated using the Bazett method (QTcB) will be summarized by treatment group. Descriptive statistics will be presented for observed values and changes from baseline at each visit where parameters were scheduled to be collected.

The number and percentage of subjects with a PCS QTcF result will be presented by treatment group and study visit. PCS results at post-baseline visits include $QTcF \ge 500$ msec, QTcF change from baseline ≥ 60 msec, QTcF change from baseline ≥ 30 msec. PCS results at post-baseline visits will also be listed.

7.5.5.3 *Ophthalmology Examination*

Standard ophthalmologic examination and corneal specular microscopy examination results will be summarized by presenting shift from baseline to end of study results as normal, abnormal not clinically significant, and abnormal clinically significant. Clinically significant abnormalities on ophthalmologic exam will be listed by treatment group, subject, and visit date.

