7.5.5.7 Columbia Suicide Severity Rating Scale

Suicidality data collected on the C-SSRS at screening, baseline, and by visit during the treatment period will be listed for all subjects. Listings will include all data collected on the C-SSRS.

At screening visit, the number and percentage of subjects with a response of 'Yes' to:

- Any Suicidal Ideation from questions #1-3 (#1: Wish to be dead, #2: Nonspecific active suicidal thoughts, #3: Active suicidal ideation with any methods (not plan) without intent to act) for the past 3 months and each individual question #1-3 will be presented by treatment group
- The Preparatory Acts or Behavior question for the past 12 months will be presented by treatment group
- Any suicide attempts (Actual Attempt, Interrupted Attempt, or Aborted Attempt) in past 12 months will be presented by treatment group

At each of the scheduled visits following screening visit, the number and percentage of subjects with a response of 'Yes' to

- Any Suicidal Ideation from questions #1-5 (#1: Wish to be dead, #2: Nonspecific active suicidal thoughts, #3: Active suicidal ideation with any methods (not plan) without intent to act, #4: Active suicidal ideation with some intent to act, without specific plan, #5: Active suicidal ideation with specific plan and intent) or any Suicidal Behavior from questions for Actual Attempt, Interrupted Attempt, Aborted Attempt, or Preparatory Acts or Behavior will be presented by treatment group.
- Any Suicidal Ideation from questions #1-5 (#1: Wish to be dead, #2: Nonspecific active suicidal thoughts, #3: Active suicidal ideation with any methods (not plan) without intent to act, #4: Active suicidal ideation with some intent to act, without specific plan, #5: Active suicidal ideation with specific plan and intent) and each individual question #1-5 will be presented by treatment group.
- Any Suicidal Behavior from questions for Actual Attempt, Interrupted Attempt, Aborted Attempt, or Preparatory Acts or Behavior and each individual question will be presented by treatment group.

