k Serum pregnancy test is to be performed at screening visit only and urine pregnancy tests will be performed by the site at all subsequent visits.

1				
m				

- Unscheduled hepatic monitoring testing may be performed at any time on the basis of clinical laboratory testing results, after consultation with the Sponsor-designated medical monitor (see Section 6.3.2.2 of the protocol).
- 0 The C-SSRS Baseline version will be used at Screening and "Since Last Visit" version will be used for all subsequent visits.
- р Adverse events reported before first dose of study drug to be recorded as medical history. Serious AEs will be recorded on the AE eCRF from the time of informed consent.
- q Subjects will be instructed to take their study drug daily in the morning and preferably with food.
- Subjects will take their first dose of study drug (BTRX-335140 or placebo) under the supervision of clinical study personnel during the baseline visit. s
- t The Week 12 corneal specular microscopy should be completed for all subjects (ie, completers and early termination) unless consent is withdrawn. The corneal specular microscopy should be conducted approximately 12 weeks after the first dose of study drug; exceptions to be discussed with the medical monitor.

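### The scheduled-visit-first window rule can leave an unscheduled C-SSRS 'Yes' out of every C-SSRS table, and affects other by-visit threshold counts to a smaller degree

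*SAP*

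**What the plan says.** SAP 7.1.2 covers efficacy analyses and by-visit safety analyses. It states that "assessments at scheduled and unscheduled visits will be mapped to the appropriate analysis window as detailed in Table 3 and Table 4". If more than one visit lands in a window, the first tie-break is "If there is a scheduled visit in the analysis window, then the scheduled" record is taken. Unscheduled data are used only when the window holds no scheduled visit; the record closest to the nominal day is then chosen, and the later one if two are equally close. Severity plays no part. Listings are not windowed and keep everything.

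For the C-SSRS, three further provisions matter:

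- SAP 6.4.2.9 says suicide-related events "are assessed and evaluated at every scheduled and unscheduled visit".
- SAP Appendix A, footnote o, says the 'Since Last Visit' "version will be used for all subsequent visits" after screening. Protocol 6.3.7 agrees.
- SAP 7.5.5.7 defines the post-screening tables as follows: "At each of the scheduled visits following screening visit, the number and percentage of subjects with a response of" 'Yes' to the ideation and behavior items. No across-visit summary is specified.

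Other threshold or category data are also presented by visit: PCS laboratory results (SAP 7.5.4), PCS vital signs (7.5.5.1), PCS QTcF (7.5.5.2), COWS of 5 or more (7.5.5.8), and eye-examination shifts (7.5.5.3, made by-visit in SAP Addendum 5.3.1.1). Extra eye examinations "may be conducted at any time during the study to assess subject safety" (SAP 6.4.2.8).

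Two summaries are handled differently. The laboratory shift table uses the worst post-baseline value, "defined as the value numerically farthest outside of the normal range across all post-baseline visits". The orthostatic blood-pressure summary uses any post-baseline measurement.

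**The concern.** Preferring the scheduled record is reasonable for a mean or a mean change, because it keeps visit timing comparable between arms. It suits yes/no and threshold data poorly, since the question there is whether the event happened at all. If an unscheduled assessment is made because of a symptom or finding, the rule discards the more informative record.

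The C-SSRS is most exposed. A persistent laboratory abnormality may show again at the next scheduled visit, but a 'Since Last Visit' form need not repeat an event already recorded at an intervening unscheduled visit. With no any-post-baseline row, nothing in the C-SSRS tables brings the event back. In a depression trial these tables are where a reader compares suicidality between arms, and listings give no by-arm counts.

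**Working it through.** The plan states no figure to reproduce. The check applies the SAP 7.1.2 rule to the windows in SAP Table 4 (Addendum Table 2 for the standard eye examination).

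**Inputs.** Nominal visit days are 15, 29, 43 and 57, each ±2 days (schedule of procedures), with the telephone contact at Day 71. Assumptions: last dose on Day 57, so last dose + 30 = Day 87; ±2 days for the telephone contact; corneal microscopy on Days 85 to 87. Post-dose days: 87 − 2 + 1 = 86.

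**Question.** On how many of these 86 days would an unscheduled record reach a by-visit table, for a subject who attends every scheduled visit?

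| Assessment | Windows (days) | Length in days | Scheduled visit in each window | Days on which an unscheduled record is used |
|---|---|---|---|---|
| C-SSRS | 2–22, 23–36, 37–50, 51–64, 65–87 | 21 + 14 + 14 + 14 + 23 = 86 | 15, 29, 43, 57, 71 | 0 of 86 |
| Vital signs, laboratory, COWS | 2–22, 23–36, 37–50, 51–87 | 21 + 14 + 14 + 37 = 86 | 15, 29, 43, 57 | 0 of 86 |
| ECG | 2–43, 44–87 | 42 + 44 = 86 | 29, 57 | 0 of 86 |
| Standard eye examination | 2–14, 15 onward | 13 + 73 = 86 | early examination by Day 14; Day 57 | 0 of 86 |
| Corneal microscopy | 2 onward | 86 | Day 85 | 0 of 86 |

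The windows leave no gap, and shifting visits within the stated tolerances does not change these results.

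**Exceptions.** If the Week 4 C-SSRS is missed, an unscheduled form on Days 23 to 36 can be used: 14 of 86 days. If the early eye examination falls on Day 15 or 16, as the protocol's two-day allowance permits, window 2–14 holds no scheduled record. An unscheduled examination there can then be used: 13 of 86 days.

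**Tracing one C-SSRS case.**

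1. Day 29, scheduled: all items 'No'. Week 4 window.
2. Day 33, unscheduled: 'Yes' to item 3. Same window, so the Day 29 record is kept.
3. Day 43, scheduled: if the form looks back only to Day 33 and nothing new has occurred, 'No'. Week 6 window.

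Every C-SSRS table shows this subject as negative. The Day 33 'Yes' is in the listing only, unless it was also reported as an AE.

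**After the change.** With an any-post-baseline row that includes unscheduled forms, a 'Yes' on any of the 86 days is counted once.

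**The case against.** The strongest reply is that the rule governs by-visit tables only, and other outputs catch most of what matters.

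- **ECG and eye findings.** A reader might infer that these disappear from the safety tables. The documents do not support that. Protocol 6.3.1 says clinically significant laboratory, vital-sign, ECG and eye findings should be recorded as AEs. Protocol 6.3.5 gives QTcF of 500 msec or more, or a rise of 60 msec or more, as examples. Treatment-emergent eye disorders are AESIs (Protocol 8.4) and are tabulated by arm (SAP 7.5.1). This largely stands. It does not extend clearly to the lower PCS threshold in SAP 7.5.5.2, a QTcF rise of 30 msec or more, which 6.3.5 does not name.
- **Discontinuation for suicidality.** A reader might infer that a subject withdrawn for ideation with a plan would be tabulated nowhere. Protocol 4.4 places such withdrawals under the Adverse Event reason, so the subject should appear in disposition and ordinarily among TEAEs leading to discontinuation. This stands. The exposed case is a 'Yes' that neither ends participation nor is reported as an AE. Protocol 6.3.1 does not list C-SSRS results among findings to record as AEs.
- **Loss is conditional.** It needs a scheduled visit in the same window. Subjects who stop early leave later windows open to unscheduled records. This stands.
- **The lookback.** The documents name the 'Since Last Visit' form but do not say whether an unscheduled contact resets it. A later form might therefore repeat the event; it is not required to.
- **No contradiction.** The laboratory shift and orthostatic summaries are across-visit analyses outside the by-visit rule, so the SAP is not inconsistent with itself. They show only that an across-visit summary was considered useful elsewhere. Protocol 9.3.4.8 planned C-SSRS listings alone, so the SAP tables already go further.
- **Frequency.** The documents expressly foresee unscheduled C-SSRS, eye examinations and repeat laboratory tests. They do not expressly foresee unscheduled post-baseline ECGs or COWS.

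**Conclusion.** The point holds for the C-SSRS. As written, an unscheduled 'Yes' is left out of the by-visit table whenever its window contains a scheduled form, and it can be missing from every C-SSRS table. This rests on the later form not repeating the event, on the absence of an any-post-baseline row, and on the event neither being reported as an AE nor leading to discontinuation. For a subject with full attendance the exposure covers all 86 post-dose days under the stated timing assumptions.

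For PCS QTcF, PCS vital signs, PCS laboratory results, COWS of 5 or more, and eye-examination categories, the mechanism is the same but the consequence is smaller. Clinically significant ECG, laboratory, vital-sign and eye findings have the AE or AESI route, and laboratory shifts and orthostatic blood pressure already use worst or any post-baseline values.

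The number of unscheduled assessments is not given. The size of the under-count, and whether it would differ between arms, cannot be stated. The primary efficacy result does not depend on this change.

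**What to change.** Keep scheduled-visit-first in SAP 7.1.2 for descriptive means and changes from baseline. Then add:

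1. In SAP 7.5.5.7, an any-post-baseline row for ideation (items 1–5, any and each) and for behavior (any and each), counting each subject once across scheduled and unscheduled assessments.
2. Matching any or worst post-baseline rows, also including unscheduled assessments, for PCS QTcF, PCS vital signs, PCS laboratory results, COWS of 5 or more, and the eye-examination category.
3. A sentence saying which record is used when two scheduled records share a window. SAP 7.1.2 is silent on this. It can arise when an end-of-treatment visit falls in the same window as the previous visit, or when an early eye examination on Day 15 or 16 shares the open-ended window with Week 8.

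The cost is SAP wording and modest programming; no new data are needed. If unblinding has already taken place, the rows can be added and documented in the clinical study report as a departure from the SAP, which SAP section 4 provides for. The downside is that counts will partly reflect who had extra assessments. The by-visit rows should therefore stay alongside the new ones, and the number of unscheduled assessments should be reported by arm.

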- ^g At Screening, collect height for BMI calculation.
- ^h Ophthalmologic examinations will be performed by a site-affiliated ophthalmologist. Details for the standard ophthalmologic examination and corneal specular microscopy will be described in a separate ocular monitoring manual. Additional standard ophthalmologic exams and / or corneal specular microscopies may be conducted to assess subject safety.

BTRX-335140 Clinical Study Protocol Amendment 7

- ⁱ Baseline ophthalmologic examinations (standard and corneal specular microscopy) must be performed before randomization.
- ^j Prior to Visit 3 (Week 2) (between Days 7 and 14 [+2 days]), a standard ophthalmologic examination will be performed.
- ^k Serum pregnancy test is to be performed at screening visit only and urine pregnancy tests will be performed by the site at all subsequent visits.
- ^m Optional assessment; subject refusal to perform will not prohibit study participation.
- ⁿ Unscheduled hepatic monitoring testing may be performed at any time on the basis of clinical laboratory testing results, after consultation with the Sponsor-designated medical monitor (see Section 6.3.2.2).
- ^o The C-SSRS Baseline version will be used at Screening and "Since Last Visit" version will be used for all subsequent visits.
- ^p Adverse events reported before first dose of study drug to be recorded as medical history. Serious AEs will be recorded on the AE eCRF from the time of informed consent.
- ^q Subjects will be instructed to take their study drug daily in the morning and preferably with food.
- ^r Subjects will take their first dose of study drug (BTRX-335140 or placebo) under the supervision of clinical study personnel during the baseline visit.
- s
- ^t The Week 12 corneal specular microscopy should be completed for all subjects (ie, completers and early termination) unless consent is withdrawn. The corneal specular microscopy should be conducted approximately 12 weeks after the first dose of study drug; exceptions to be discussed with the medical monitor.

BTRX-335140	BlackThorn Therapeutics, Inc.
Clinical Study Protocol Amendment 7	Date: 24Jan2022

TABLE OF CONTENTS

CL	INICAL ST	TUDY PROTOCOL: K2-MDD-201	1
SP	ONSOR SI	GNATURE	2
IN	VESTIGAT	FOR AGREEMENT	3
SU	MMARY (OF CHANGES	4
SY	NOPSIS		5
SC	HEDULE (OF PROCEDURES AND ASSESSMENTS	11
TA	BLE OF C	ONTENTS	14
LIS	ST OF TAE	BLES	
LIS	ST OF FIG	URES	
LIS	ST OF APP	ENDICES	
LIS	ST OF ABE	BREVIATIONS	19
1	IN	TRODUCTION	
	1.1	Background Information	

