Subjects who meet the DSM-5 diagnostic criteria for MDD and all other eligibility criteria for the study will be randomized in a 1:1 ratio to 1 of 2 treatment arms (placebo or BTRX-335140 QD) until approximately 180 subjects are randomized. Beginning at Visit 2 (Baseline), subjects will receive treatment with BTRX-335140 80 mg QD or placebo for 8 weeks. During the Safety Follow-up, all subjects will receive a telephone call (TC) from study site personnel approximately 2 weeks after discontinuation of study drug for assessment of AEs, concomitant medication usage, and C-SSRS; and at Week 12, subjects will have corneal specular microscopy performed by a study site-affiliated ophthalmologist. The overall duration in the study for each subject is expected to be approximately 14 to 16 weeks.

The Week 12 corneal specular microscopy should be completed for all subjects (ie, completers and early termination) unless consent is withdrawn. The corneal specular microscopy should be conducted approximately 12 weeks after the first dose of study drug; subjects who terminate the study early would need to plan for the corneal specular microscopy at 12 weeks after the first dose of study drug. Any exceptions are to be discussed with the medical monitor.

Additional ophthalmologic examinations (standard ophthalmologic exams and/or corneal specular microscopies) may be conducted to assess subject safety.

Details of study procedures and assessments are provided in Section 6; for details on the timings of study assessments refer to Section 7 and the Schedule of Procedures and Assessments.

Study sites will maintain, at a minimum, coronavirus disease 2019 (COVID-19) risk mitigation procedures as per regulatory and local guidelines and/or laws. Allowed modifications to the conduct of the study, in the event of site staff and/or patient restrictions due to COVID-19, are outlined in Appendix 1.

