7.6 Visit 6: Week 8 (Day 57)/End of Treatment

Special effort will be made by the site to encourage subjects who discontinue from the study early to complete all Visit 6 (Week 8) safety assessments (within 2 days of their last dose of study drug), the Safety Follow-up TC, and ophthalmologic examinations (Section 7.8); efficacy assessments are to be performed only if the subject has remained on study drug. If the subject does not attend the discontinuation visit, the C-SSRS should be completed if the site has become aware of a potential suicide-related thought or behavior by other communications.

BTRX-335140	BlackThorn Therapeutics, Inc.
Clinical Study Protocol Amendment 7	Date: 24Jan2022

Additional ophthalmologic examinations (standard ophthalmologic exams and/or corneal specular microscopies) may be conducted to monitor subject safety.

The following order of procedures is recommended to prioritize safety and efficacy assessments:

- 1. Breathalyzer test for blood alcohol level
- 2. Subject and investigator will conduct/administer the following assessments on the tablet supplied:
 - a. HAMD-17
 - b. HAM-A
 - c. Allow subject to complete SHAPS; reviewed by site personnel qualified to oversee completeness
 - d. e.
 - f. Allow subject to complete HADS; reviewed by site personnel qualified to oversee completeness
 - g. Allow subject to complete SDS; reviewed by site personnel qualified to oversee completeness
 - h. C-SSRS 'Since Last Visit' version
 - i. CGI-I and CGI-S
 - j. k.
- 3. Concomitant therapies review and reporting
- 4. AE reporting
- 5. Physical examination if indicated
- 6. Weight
- 7. Vital signs (respiratory rate, BP, and pulse [supine and standing]; temperature)
- 8. COWS
- 9. 12-lead ECG
- 10. Standard ophthalmologic examination (± 2 days) (refer to Section 6.3.6)
- 11. The subject-returned investigational study drug will be accounted for.
- 12. Complete IWRS

BTRX-335140	BlackThorn Therapeutics, Inc.
Clinical Study Protocol Amendment 7	Date: 24Jan2022

13. Blood and urine collection for central laboratory analysis (including urine drug screen for all subjects and urine pregnancy test for women of child-bearing potential)

14.

The investigator will review the results of the central laboratory tests for safety in a timely manner.

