7.7 Safety Follow-up

7.7.1 Telephone Call (Week 10)

Subjects will receive a TC from the study site approximately 2 weeks after the last dose of study drug to inquire about AEs and concomitant medication usage, and will administer the C-SSRS.

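### C-SSRS windows count from first dose but the follow-up call is timed from last dose, so off-drug calls of subjects who stop by about Day 50 are tabulated in treatment weeks

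*SAP*

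**What the plan says.** SAP 7.1.2 states that "assessments at scheduled and unscheduled visits will be mapped to the appropriate analysis window". For C-SSRS, Table 4 gives Week 2 as Days 2–22, Week 4 as 23–36, Week 6 as 37–50 and Week 8 as 51–64, all under the column header Study Drug Treatment. Week 10, under Safety Follow-up, is "65, last dose +30". Only the C-SSRS screening cell is mapped by nominal visit.

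The protocol times the call differently. Section 7.7.1: "Subjects will receive a TC from the study site approximately 2 weeks after the last dose of study drug". Section 3.1 extends this to everyone: "all subjects will receive a telephone call (TC) from study site personnel approximately 2 weeks after discontinuation of study drug", with the C-SSRS among the assessments made. Early terminators are also encouraged to complete the end-of-treatment safety assessments "within 2 days of their last dose of study drug" (Section 7.6).

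SAP 7.5 keeps safety data up to 30 days after last dose, so the call is analysed. SAP 7.5.5.7 tabulates C-SSRS responses by visit and treatment group, and SAP 7.1.1 bases percentages on subjects with available data.

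For corneal specular microscopy, Table 4 has one post-baseline window, Day 2 or later, labelled Week 12. The protocol's schedule (footnote h) says: "Additional standard ophthalmologic exams and / or corneal specular microscopies may be conducted to assess subject safety". The SAP addendum (5.1.1) changes only the windows for the standard ophthalmologic examination.

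**The concern.** A visit row in a suicidality table is normally read as the state of subjects at that point in treatment. Here a subject who stopped early can contribute an off-drug telephone assessment to a row headed as drug treatment. Such a record enters both the numerator and the denominator of the percentage for that week. The follow-up row, where a reader would look for post-treatment suicidality, then lacks most of those who stopped early.

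This matters because Protocol 6.3.7 itself names the time soon after stopping an antidepressant as one in which suicidal events have been reported. If the end-of-treatment visit took place on time, the call's recall period is almost wholly off drug, since every C-SSRS after screening asks about the time since the previous visit. The planned tables do not separate that period from time on drug.

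The corneal row raises a smaller question of the same kind: a result labelled Week 12 may come from any time after Day 1.

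**Working it through.** **Reproducing the plan's cut-points.** Nominal visit days are 15, 29, 43, 57 and 71. Midpoints: (15+29)/2 = 22; (29+43)/2 = 36; (43+57)/2 = 50; (57+71)/2 = 64. These are the upper bounds in Table 4 for Weeks 2, 4, 6 and 8. The windows are therefore built for a subject who follows the full schedule, with the call near Day 71.

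**Mapping the call.** Let L be the study day of last dose. Taking 'about 2 weeks' as 14 days, the call falls on Day L + 14.

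| Last dose L | Call day L + 14 | Table 4 row |
|---|---|---|
| 1–8 | 15–22 | Week 2 |
| 9–22 | 23–36 | Week 4 |
| 23–36 | 37–50 | Week 6 |
| 37–50 | 51–64 | Week 8 |
| 51–56 | 65–70 | Week 10 |

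For example, last dose on Day 14 gives a call on Day 28, counted in Week 4. Last dose on Day 42 gives a call on Day 56, counted in Week 8.

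**Sensitivity to call timing.** A call g days after last dose is placed in a treatment week if L + g ≤ 64, that is L ≤ 64 − g. For g = 12, 14 and 16 the cut-off is Day 52, 50 and 48.

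**The Week 10 window.** It contains a day only if L + 30 ≥ 65, so L ≥ 35. For L ≤ 34 it is empty. A call at L + 14 would then fall no later than Day 48 and could not reach Day 65 anyway. The empty window is a consequence of the same mismatch and excludes no further planned call.

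**Two scheduled contacts in one row.** If the end-of-treatment visit is on Day L, it shares Week 2 with the call for L = 2–8. If it is on Day L + 2, the two share a row for L = 1–8, 21, 22, 35, 36, 49 and 50. The selection rules in SAP 7.1.2 prefer a scheduled over an unscheduled record, but do not choose between two scheduled ones.

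**Corneal microscopy.** The planned image is at about Day 85. The window opens on Day 2, so an image up to 85 − 2 = 83 days early qualifies. Because a scheduled record takes precedence, this happens only for a subject with an unscheduled image and no scheduled one.

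**The case against.** The strongest reply is that the SAP never says the Week 2 to Week 8 rows are on-drug results. The header marks time since first dose, safety data are deliberately kept to 30 days after last dose, and a call 14 days after last dose is within that scope. Listings are not windowed and carry all C-SSRS data, so each event can be set against the last dose date. Protocol 9.3.4.8 promised only a listing; the by-visit counts are an SAP addition with no test attached.

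Most of this stands, and it limits the point to labelling in descriptive tables. It does not remove it. Being in scope for analysis does not make Week 4 of treatment the right row for an off-drug call, and a table user will not rebuild the rows from listings.

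On the corneal row, a reader might infer that the wide window biases endothelial cell loss toward zero, in the very subjects most likely to miss Week 12. The documents support neither step. Nothing links early unscheduled images to missing the Week 12 examination. Extra images are taken for safety, and Protocol 6.3.6 allows additional examinations after an ocular event of special interest, so they may over-represent abnormal eyes. The direction is unknown. Early terminators are also asked to return at about 12 weeks, and SAP 7.5.5.3 words the cell-density summary as post-baseline rather than Week 12. The exposure is narrow.

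**Conclusion.** The C-SSRS point holds. As written, Table 4 puts the follow-up call of anyone whose last dose is on or before about Day 50 (Day 48 to 52, depending on call timing) into a treatment-week row, and leaves the follow-up row to completers and very late terminators. This assumes the call is made on the protocol's timing and that no mapping rule exists outside the documents. If the end-of-treatment visit was missed, the call's recall also reaches back into time on drug, so not every misplaced record is purely off-drug.

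The number of affected records cannot be computed: the documents give no number of early terminators. No primary or inferential result is touched, and no individual event is lost. A reader might take the empty Week 10 window as a second defect, or conclude that post-discontinuation events are hidden; neither follows.

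The corneal point holds as a secondary labelling problem, confined to subjects with an unscheduled image and no scheduled one, and without a claim about the direction of bias.

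**What to change.** In Table 4, map the C-SSRS from the follow-up call to the Safety Follow-up row by nominal visit, whatever the study day, as the screening cell already is. Limit the Week 2 to Week 8 rows to scheduled treatment or end-of-treatment visits and to unscheduled assessments made before that call. This also settles which record is used when the end-of-treatment visit and the call share a window. Capping the treatment rows at 2 days after last dose is less suitable, because a late end-of-treatment visit would then be misplaced.

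For corneal microscopy, either relabel the row as post-baseline, or give Week 12 a lower bound near Day 85 and show earlier unscheduled images separately. While that row is open, reconcile it with SAP 7.5: a Day 85 image lies beyond last dose + 30 for any last dose before Day 55 (85 − 30 = 55), yet the window has no upper limit.

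The cost is small: a revised mapping for two assessments, one additional display row, and a few fewer records in the treatment-week and Week 12 rows. No new data are needed.
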